Previous studies have reported that smoking abstinence rates are increased when nicotine skin patch treatment is initiated prior to the target quit smoking date, as compared with conventional treatment beginning on the quit date. Rose et al (2009) showed that continuous abstinence rates were approximately doubled by pre-cessation nicotine patch treatment (22% vs. 11%). The treatment which was well tolerated mainly benefited smokers with lower levels of dependence. The authors hypothesized that smoking in the presence of continuous levels of nicotine attenuated the reinforcing effects of cigarette smoking and led to a decline in dependence on inhaled nicotine, thus facilitating cessation.

Lorcaserin (Belviq) is a selective serotonin 2C (5-HT2C) receptor agonist which decreases body weight by selectively mimicking the effects of serotonin at the 5-HT2C receptor. Serotonin is a monoamine neurotransmitter which acts on the central nervous system to reduce food intake. The FDA approved Belviq in 2012 for chronic weight management in adults with a BMI of >30 kg/m² or >27 kg/m² with a comorbid condition.

Bubar et al (2007) reported that the 5-HT2C receptor may be important in inhibiting dopaminergic neurons (which are important for drug reinforcement) in the ventral tegmental area. This inhibition of dopaminergic neurons suggests that lorcaserin HCl may have an effect on smoking cessation (Higgins et al, 2013). Two investigators have studied the ability of lorcaserin to inhibit nicotine self-administration in rats.

In a study conducted by Levin et al (2011)., lorcaserin HCl (0.625 mg/kg subcutaneous [SC]) was found to decrease nicotine self-administration ~50%, with no sign of

attenuation of effect after 10 doses; at this dose, there was no effect on food-motivated responding and no generalized locomotor hypoactivity. In a separate study conducted by Higgins et al (2012), lorcaserin HCl reduced feeding behavior and self-administration of nicotine in the same dose range (0.6-1 mg/kg SC).

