Blood and urine specimens will be sent to LabCorp for processing. The results of laboratory blood and urine tests will not routinely be given to participants to send or be sent to their physician to include in their medical record. However, if the subject's lab results are outside the acceptable range for participation in the study the Physician/P.A. will send the subject a medical exclusion letter and a copy of the lab results. Participants who are accepted into the study but need medical follow up due to minor abnormalities in lab results will also be informed by letter from the Physician/P.A. A copy of the laboratory results will be included with the letter, which will also indicate that the condition does not interfere with his/her participation in the study.

The time commitment for subjects is 16 weeks: 4 weeks of pre-cessation treatment before the scheduled Quit Day and 12 weeks of additional post-Quit Day treatment, plus one follow-up session at six months (if eligible) after the Quit Day.

Questionnaires will be completed within REDCap on a desktop computer in the Center office. The technician will log on to the REDCap site and will open the questionnaires for the subjects. Subjects will only have access to their questionnaires. Access to any other websites will be blocked by Psychiatry Information Technology.

Session P1

The first study visit will take place approximately one week after the screening visit. Subjects will complete baseline questionnaires and will be randomized to either Group A (nicotine patch + lorcaserin) or Group B (nicotine patch + placebo). Subjects will be tested for exhaled air carbon monoxide and smoking related chemicals in the saliva. They will also have their blood pressure, heart rate and weight measured. Females of child bearing potential will also complete a urine pregnancy test which must be negative in order to continue study participation. Subjects will also complete questionnaires rating craving, withdrawal symptoms, side effects, and sensory experience.

Subjects will be given a supply of study medications (depending on randomization) to use for 2 weeks and will receive verbal and written instructions on how to take them.

Subjects will also be given diaries to record medication use and the number of cigarettes smoked each day and will be instructed to return the diaries at the next visit. They will also be asked to return any unused medications for proper disposal and compliance monitoring.

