DATA ANALYSIS & STATISTICAL CONSIDERATIONS

The primary outcome measure will be the time-to-lapse during the laboratory session. McKee et al. (2012) reported an effect size of ~0.8 on this measure, and obtained significant results assessing the therapeutic effects of bupropion and varenicline with n=20 per group. With n=30 per group in the proposed study, and using a one-tailed alpha=0.05 (the hypothesis is one-tailed inasmuch as there would be no interest in pursuing the development of lorcaserin unless an increase in time-to-lapse is demonstrated), we should obtain over 90% power to detect a comparable effect. Secondary outcomes that will be compared between groups include the percent reduction in ad libitum smoking during the first 2 weeks, and withdrawal symptoms reported after 2 hours of smoking abstinence in the laboratory, measures that have been sensitive to treatment in our previous studies of nicotine replacement therapy (NRT) and other treatments. The two treatment groups will be compared on these measures using ANOVA-based statistical methods.

Continuous abstinence from smoking during weeks 7-10 after the quit date will also be tabulated, and 90% confidence intervals will be calculated. Abstinence will also be correlated with the reduction in ad libitum smoking in the first 2 weeks to determine whether smoking reduction may be a useful early marker of therapeutic efficacy. Among smoking-abstinent participants, weight gain relative to baseline will also be assessed, and 90% confidence intervals will be calculated.

Tolerability of treatment will be assessed by tabulating side effect frequencies and degree of adherence to taking medications (percent of total doses taken, assessed by self-report diaries and counts of returned medications at each session).

DATA & SAFETY MONITORING

Description of BP monitoring procedures after study enrollment

After study enrollment, if blood pressure during return sessions is above 160/100, then the following actions will be taken to enhance subject safety:

- If BP >210/100 with symptoms of malignant hypertension: stop experiment interventions and refer to appropriate medical treatment. Resume participation and continue to be monitored if BP is no greater than 140/100.

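### No baseline covariate is pre-specified for the primary time-to-lapse comparison, although smoking level and expired CO are recorded before any drug and adjustment would cost almost nothing

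*Combined protocol and SAP*

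**What the plan says.** All references are to the combined protocol and SAP.

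- **Primary comparison** (Data Analysis & Statistical Considerations): "The primary outcome measure will be the time-to-lapse during the laboratory session". The sample size rests on a cited laboratory study that "reported an effect size of ~0.8 on this measure". The text continues: "With n=30 per group in the proposed study, and using a one-tailed alpha=0.05", and concludes "we should obtain over 90% power to detect a comparable effect".
- **Method** (same section): "The two treatment groups will be compared on these measures using ANOVA-based statistical methods". This sentence follows the list of secondary outcomes, so whether it also covers the primary outcome is a matter of reading. On either reading no covariate is named.
- **Allocation** (Session P1): "Subjects will complete baseline questionnaires and will be randomized to either Group A (nicotine patch + lorcaserin) or Group B (nicotine patch + placebo". No stratification factor is mentioned here or in the Design Overview.
- **Dependence** (Background & Significance), on an earlier trial of patch started before the quit date: "The treatment which was well tolerated mainly benefited smokers with lower levels of dependence". The outcome reported there is continuous abstinence, 22% against 11%.
- **Data available before drug**: smoking history and expired CO at screening (Screening and Session Procedures), and CO again at P1. Entry requires an average of at least 10 cigarettes per day, with no upper limit (Inclusion Criteria).

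**The concern.** Both arms wear the 21 mg patch for the two weeks before the P2 session. If dependence affects how smokers respond to that patch, or how long they can hold out in the laboratory, it is a source of variation in time-to-lapse that has nothing to do with lorcaserin. The outcome has no baseline value of its own to absorb such variation, and the plan names no substitute.

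The plan says development of lorcaserin would not be pursued unless time-to-lapse increases, so one one-tailed comparison in about 60 people carries much weight. If the arms turn out to differ in smoking level, the investigators face two poor choices: an unadjusted result that invites challenge, or an adjustment chosen after the imbalance was seen.

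**Working it through.** **Inputs from the plan.** n = 30 per arm, standardised effect d = 0.8, one-tailed alpha 0.05.

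**Assumptions (not in the documents).** Correlation r between baseline covariate and time-to-lapse, 0.1 to 0.4. A loss case of 26 per arm. For the imbalance check, a factor splitting the 60 participants 30/30 and worth 0.5 to 0.8 SD of time-to-lapse.

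**1. The plan's own figure.** Noncentral t with df = 58 and noncentrality d·√(n/2) = 0.8 × √15 = 3.098; the critical value is 1.672. Power is 92.2%. The normal approximation gives 92.7%. The claim of more than 90% reproduces.

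**2. Power with adjustment.** Residual SD shrinks by √(1 − r²), so the effective d is 0.8/√(1 − r²), with one degree of freedom lost.

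| r (assumed) | 30 per arm | 26 per arm (assumed) |
|---|---|---|
| unadjusted | 92.2% | 88.5% |
| 0.1 | 92.4% | 88.8% |
| 0.2 | 93.0% | 89.6% |
| 0.3 | 94.1% | 90.9% |
| 0.4 | 95.5% | 92.8% |

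A second lost degree of freedom moves none of these by more than about 0.1 point. The formula ignores the small cost of estimating the slope. In simulation (40,000 trials per case, one covariate) adjusted power was 92.8% at r = 0.2 and 93.8% at r = 0.3. At r = 0 it was 91.5%, against 92.0% unadjusted, so a useless covariate costs about half a point.

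If the true effect were d = 0.5 (assumption), power at 30 per arm would go from 60.6% to 64.1% at r = 0.3.

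**3. How often the arms differ.** Suppose 30 of 60 are in the more dependent half and allocation is not stratified on that factor. The number of less dependent smokers in the lorcaserin arm is then hypergeometric (60, 30, 30). A gap of 20 percentage points means 18 against 12. P(18 or more) = 9.8% favours lorcaserin, and P(12 or fewer) = 9.8% goes against it. Together that is 19.6%.

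**4. What such a gap does to the unadjusted test.** The arm difference shifts by 0.20 × 0.5 = 0.10 SD, or by 0.20 × 0.8 = 0.16 SD.

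| Shift | False-positive rate, gap favours lorcaserin | False-positive rate, gap against | Power at d = 0.8, gap against |
|---|---|---|---|
| 0.10 SD | 10.3% | 2.1% | 85.0% |
| 0.16 SD | 15.1% | 1.2% | 79.0% |

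Simulation at exactly a 20-point gap is slightly milder: 9.7-13.1% false positives when the gap favours lorcaserin, and power of about 86% or 81% when it goes against.

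For a 30/30 split a gap of 0.5-0.8 SD corresponds to r = 0.5 × 0.5 = 0.25 up to 0.5 × 0.8 = 0.40, so this table belongs with the upper part of the range in step 2.

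**5. Overall error.** Over all allocations, simulated type I error of the unadjusted test was 5.0-5.1%. Within the 19.6% of trials with a gap either way, the average of the two directions is 6.2% (0.10 SD) or 8.1% (0.16 SD).

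**The case against.** The strongest reply is that an unadjusted randomised comparison is valid. Chance imbalance is already part of what alpha covers, there is no systematic bias, and the trial is a small pilot whose power claim holds as written. All of that stands. At r = 0.1-0.2 the gain with full enrolment is under one point.

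It is also fair that the background does not tie dependence to this outcome. The cited result concerns abstinence and the benefit of starting the patch early; it is not about delay in an incentive task among smokers who all wear patches. A reader might infer that dependence is a known predictor of time-to-lapse, or that it governs response. The documents support only that it is plausible. No dependence scale is named, so cigarettes per day and CO are proxies, and the entry thresholds (10 per day, 10 ppm) may weaken their correlation with the outcome.

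Finally, silence is not a negative. The ANOVA wording does not rule out a covariate, and the randomisation method is not described at all. The accurate statement is that none is pre-specified.

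What survives is the choice itself. Long-run error control does not help interpret the one allocation that occurs, and a covariate named in advance removes the dispute at almost no cost.

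**Conclusion.** The point holds as a matter of precision and pre-specification; the primary test is not in error. The plan's power figure stands at 92.2%. Adjustment adds less than one point for r of 0.1-0.2 and about two to three points for 0.3-0.4. It matters more if participants are lost: the sample-size text makes no allowance for loss, and the Emergency Unblinding section removes any unblinded participant from the analysis. At 26 per arm, r of 0.3-0.4 is enough to bring power back above 90%; r of 0.1-0.2 is not.

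A reader might infer that the trial's false-positive rate is really 10-15%, or that this rate applies to every trial with a 20-point gap. Neither follows. Roughly 10-15% is the conditional one-sided rate in the 9.8% of trials where the gap favours lorcaserin. In the mirror-image 9.8% it drops to about 1-2% and the price is power. Overall it stays at 5%. Every figure beyond the plan's own 92.2% depends on assumptions about r, the size of the factor or losses that the documents cannot settle.

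**What to change.** In Data Analysis & Statistical Considerations, add one sentence: the primary time-to-lapse model, whatever its form, includes treatment arm, baseline cigarettes per day and pre-drug expired CO. State which CO reading is used (screening or P1), and fix the choice before unblinding.

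No new data are needed. The cost is one to two degrees of freedom, and there is little or no gain if the covariates turn out to be weakly related to the outcome. Stratifying the randomisation on smoking level is optional; it would need a cut value, would overlap with the covariates and is not required for this change.

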We propose to enroll up to 360 smokers in order to identify 60 participants who meet all criteria to be accepted into the study and to be randomized into one of two treatment conditions. When the 60th subject is randomized into the study, we will discontinue new recruitment efforts for the study. If there are individuals who already have screening or baseline appointments scheduled, these appointments will be honored. Thus, it is possible that our final sample will exceed 60 participants by some small number.

Inclusion Criteria

- Are 18-70 years old;
- Smoke an average of at least 10 cigarettes per day;
- Have smoked at least one cumulative year;
- Have an expired air CO reading of at least 10ppm;
- Body weight of ≥ 50 kg (110 lbs.) and ≤ 170 kg (375 lbs);
- Able to read and understand English;

- Express a desire to quit smoking in the next thirty days.

Potential subjects of child bearing potential must agree to use acceptable contraception during their participation in this study. Medically acceptable contraceptives include: (1) surgical sterilization (such as a tubal ligation or hysterectomy), (2) approved hormonal contraceptives (such as birth control pills, patches, implants or injections), (3) barrier methods (such as a condom or diaphragm) used with a spermicide, or (4) an intrauterine device (IUD). Contraceptive measures such as Plan B (TM), sold for emergency use after unprotected sex, are not acceptable methods for routine use.

Potential subjects must agree to avoid the following during their participation in this study:

- participation in any other nicotine-related modification strategy outside of this protocol;
- use of tobacco products other than cigarettes, including pipe tobacco, cigars, e-cigarettes, snuff, and chewing tobacco;
- use of experimental (investigational) drugs or devices;
- use of illegal drugs;
- use of exclusionary medications.

Exclusion Criteria

- Hypertension (systolic >140 mm Hg, diastolic >100 mm Hg, coupled with a history of hypertension); subjects with no previous diagnosis of hypertension may have a screening blood pressure up to 160/100.
- Hypotension with symptoms (systolic <90 mm Hg, diastolic <60 mm Hg).
- Participants with a history of hypertension may, however, be allowed to participate in the study if the study physician or physician assistant determines that the condition is stable, controlled by medication, and in no way jeopardizes the individual's safety.

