This is a blinded protocol such that all participants and all study personnel except for the Clinical Research Coordinator and the Research Program Leader are blinded to group allocation. During specific circumstances it will be necessary to unblind other study personnel, such as study team medical personnel. Emergency unblinding will occur under the discretion of the study physician (or one of the study physician assistants) in any situation in which unblinding is deemed necessary to ensure or promote the safety of a study participant. The decision to unblind for safety reasons may occur for a number of reasons and it is not possible to enumerate all potential circumstances. Examples of reasons for unblinding to ensure participant safety include situations in which it is necessary to know which study drugs the subject was taking in order to manage the side effect(s), advise the subject on the risk of future negative drug reactions, uncover potential safety information about the drug, and/or determine whether the adverse event

is study related. In those situations, the Clinical Research Coordinator or Research Program Leader will inform the study physician (or physician assistant handling the event) of that subject's treatment condition. If unblinding occurs, that subject's data will be censored and will not be included in final data analyses.

DATA STORAGE & CONFIDENTIALITY

Any PHI collected prior to documentation of informed consent will be de-identified if the potential subject does not qualify for this study. Please refer to the "Request for Waiver of Documentation of Informed Consent".

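### Does the claim of over 90% power fail under an ANOVA F-test, or with modest losses before the P2 laboratory session?

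*Combined protocol and SAP*

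**What the plan says.** The section Data Analysis & Statistical Considerations defines the endpoint: "The primary outcome measure will be the time-to-lapse during the laboratory session". It takes its effect size from a published laboratory study that "reported an effect size of ~0.8 on this measure" and "obtained significant results assessing the therapeutic effects of bupropion and varenicline with n=20 per group". The power statement follows: "With n=30 per group in the proposed study, and using a one-tailed alpha=0.05", "we should obtain over 90% power to detect a comparable effect". The plan justifies the one-tailed test by saying that lorcaserin would not be developed further without an increase in time-to-lapse.

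The same paragraph then lists the secondary outcomes (smoking reduction and withdrawal symptoms). It closes by saying that the groups will be compared on these measures with methods based on ANOVA. It names no F-test and no two-sided alpha.

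Two other places affect the number analysed. Subject Identification says "When the 60th subject is randomized into the study, we will discontinue new recruitment efforts for the study", and adds that appointments already booked will be honoured, so the total may slightly exceed 60. Emergency Unblinding says "If unblinding occurs, that subject's data will be censored and will not be included in final data analyses".

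**The concern.** Three features make the power figure look doubtful.

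- **The test.** If the reference to ANOVA covers the primary outcome and is read as an ordinary F-test at 0.05, the test is two-sided in effect and power is below 90%.
- **The number analysed.** Recruitment stops on the number randomised, but the endpoint is measured two weeks later. Participants may withdraw at any time, and unblinded participants are removed from the analysis. No inflation for loss is given.
- **The effect size.** The 0.8 comes from a study of bupropion and varenicline. Here both arms wear a 21 mg patch, so the contrast is the increment from adding lorcaserin. The plan offers no time-to-lapse data for that increment.

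The plan ties further development of lorcaserin to a positive primary result. If true power were well below 90%, a null result could be read as stronger evidence against the drug than it is.

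**Working it through.** **Inputs from the plan:** 30 per group, effect size about 0.8, one-tailed alpha 0.05. The plan does not name the effect-size metric; I read it as a standardised mean difference, *d*.

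**Formula.** For a two-group t-test, the noncentrality is δ = *d* × √(n₁n₂/(n₁+n₂)), with n₁+n₂−2 degrees of freedom. One-tailed power is the probability that a noncentral t with parameter δ exceeds the upper 5% point of t.

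**Step 1: the plan's own figure.** δ = 0.8 × √(900/60) = 0.8 × √15 = 3.098, with 58 df and critical value 1.672. Power is **92.2%**. The normal approximation gives Φ(3.098 − 1.645) = Φ(1.453) = 92.7%. Both exceed 90%, so the figure reproduces.

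**Step 2: the ANOVA reading.** With two groups, F on 1 and 58 df is the square of t. At 0.05 it is the two-sided t-test (critical value 2.002), and power is 86.1%. Run at 0.10 with the sign required to favour lorcaserin, it is the one-tailed 0.05 test, and power is again 92.2%. ANOVA and a one-tailed hypothesis are therefore compatible. The gap of 92.2 − 86.1 = 6.1 points comes only from dropping the declared sidedness.

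**Step 3: losses before P2.** One-tailed power at *d* = 0.8, exact t:

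| Analysed per arm | Total | Power |
|---|---|---|
| 30 / 30 | 60 | 92.2% |
| 28 / 28 | 56 | 90.5% |
| 30 / 26 | 56 | 90.4% |
| 28 / 27 | 55 | 90.0% |
| 30 / 25 | 55 | 89.8% |
| 27 / 27 | 54 | 89.5% |
| 25 / 25 | 50 | 87.4% |

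The design keeps 90% with four losses, and with five if they are split evenly. The plan gives no dropout rate, so three per arm is an assumption. Its effect is 90.0 − 89.5 = 0.5 points below the mark. The normal approximation puts the same case at 90.2%, and *d* = 0.81 at 27 per arm also gives 90.2%. The shortfall therefore lies inside the rounding of an effect size quoted as about 0.8.

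**Step 4: the effect size.** At 30 per arm the smallest *d* with 90% one-tailed power is 0.765. For smaller effects, power is 85% at 0.7, 74% at 0.6, 61% at 0.5 and 45% at 0.4. These smaller values are illustrative; none is in the documents.

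**The case for a change.** The strongest case for a change rests on the effect size. Power depends heavily on *d*, and the plan's lorcaserin evidence consists of abstinence rates, weight change and rat self-administration, not time-to-lapse on top of a patch. If the true increment were 0.5, the trial would miss it about 39% of the time (100 − 61), and the plan links a null result to stopping development. It also does not say how the one-tailed hypothesis becomes a test, which could leave the choice between a one-sided and a two-sided p-value until the data are seen.

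Part of this stands. The plan gives no argument for carrying 0.8 over to an add-on contrast, no minimum detectable effect and no margin for loss. But the statement is conditional: it claims power for an effect comparable to the published one, and for that effect it is right. The documents contain nothing from which a better value could be derived. The protocol also calls the trial small-scale and intends it as pilot data for a later, well-powered trial.

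On the test, the sidedness is declared and justified in advance. An analyst who reported a two-sided primary p-value would be departing from the plan. The sentence on ANOVA follows the secondary outcomes and may not cover the primary at all. If it does not, the method for the primary is left to be inferred, but the stated alpha still fixes its direction.

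**Conclusion.** The concern does not call for a change. The power statement is correct for its inputs: 92.2% against a claim of over 90%. The 86.1% figure belongs to a two-sided test that the plan does not specify. The fall below 90% requires an assumed loss of about three per arm and amounts to half a point. Much lower power requires smaller effects that no document supplies.

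The omissions are how the one-tailed test is carried out, the lack of an attrition allowance, and the missing argument for 0.8 in an add-on comparison. A careful analyst fills the first from the declared alpha. Stating the other two would help a reader interpret a null result, but would alter neither the sample size nor the analysis. Anyone interpreting the result should bear in mind that about 55 to 56 of the 60 must be analysed at P2 to hold 90%, and that this level applies only to effects of about 0.77 or more with all 60 analysed.

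This conclusion assumes that the published effect size is a standardised mean difference and that the primary comparison is a two-group test on means.
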